3.3 Blinding Procedure

The participants, Principal Investigator and Study Coordinators will be blinded to treatment, except in the case of an emergency that requires unblinding of a participant. In order for each Principal Investigator to remain blinded for all participants throughout the study, each site will designate a minimum of one, but no more than two, licensed members of the study staff (e.g., M.D., D.P.M., P.A., Nurse Practitioner, study assistant, etc.) to be the unblinded Treatment Administrator. The role of the Treatment Administrator(s) will be to administer the study device (both active and SHAM) and maintain and complete the Device Treatment and Training logs. In order to verify that the correct application was being used for each participant at each study visit, the code will be reviewed by the local Study Sponsor during monitoring visits and throughout the study when a participant is enrolled.

Each participant will register their user name in the mobile app and run an application for the first treatment prior to leaving the clinic. The Principal Investigator and/or designated Sub-Investigators will serve as the blinded evaluators for all study visits.

3.4 Participant Assessments

3.4.1 Screening – Visit 1

Participants will be preliminarily qualified to determine eligibility, i.e., those who meet all applicable inclusion/exclusion criteria that do not require a study related procedure to be performed. Those participants that meet the preliminary qualification and who agree to participate in the study will sign an Informed Consent. At the initial screening visit, participants will have their demographic information collected, their medical and medication history collected (including duration and severity of AGA); as well as a urine pregnancy test, for females of child bearing potential.

Demographic information will be collected as follows:

- Details including age and date of birth
- Gender
- Co-morbid conditions
- Work status
- Education level
- Smoking history

3.4.2 Baseline – Visit 2

The Baseline visit is the time remaining screening procedures will be completed, with the participant enrolled and randomised to a device, if eligible. This visit can take place up to 7 days from Visit 1, or it can be conducted the same day. Participants will have a physical examination and will then fill out a baseline Hair Specific Skindex-29 Quality of Life Questionnaire. This questionnaire is a wellestablished, three-dimensional, dermatology-specific health-related quality-of-life (HRQoL) instrument designed to evaluate the impact of androgenetic alopecia (AGA) and treatment outcome on a participant's physical, psychological, social functioning and well-being. A participant must have a Hair Specific Skindex-29 total overall score of \geq 45 at baseline to be eligible for enrollment. The Skindex-29 consists of 29 items loading on emotional (10-50), functioning (12-60) and symptom (7-35) categories with total scoring ranging from 29-145. The questions refer to the previous 4-week period, and scores are given on a 5-point scale, from 'never' to 'all the time'. Greater scores indicate poorer quality of life. The scale scores are computed by transforming responses to a 100-point scale, with higher

scores indicating a lower level of quality of life. The overall score and individual category scores will be used to demonstrate improvement over the course of the trial. Corresponding Skindex-29 cut-off scores for severely impaired HRQL are as follows: \geq 52 points on symptoms, \geq 39 on emotions, \geq 37 on functioning, and \geq 44 on the overall score. The estimated cut-off scores can be used in clinical practice to identify patients with (very) severely impaired HRQL

The Investigator will conduct a routine physical exam and record the following:

- i. Medical Assessment will be performed and the following information recorded:
- Complete history
- Physical Exam (including vital signs)
- Previous treatments for AGA
- Co-morbid conditions and any disabilities
- Duration and severity of AGA
- Concomitant medication usage
- Pregnancy Test urine dipstick (as required)
- ii. Assessments and Procedures will be collected as follows:
 - Hair Specific Skindex-29 Quality of Life Score Questionnaire

If a participant remains eligible, the Investigator will enter the participant into the study. Eligible participants will then have photographic assessments conducted and be trained on the components and use of REVIAN/SHAM and will undergo the first treatment at the PI's office. The day of the first treatment will be considered as the date of participant enrollment.

- Global Photography Image of Two Views (superior and vertex scalp)
- Shave and Tattoo Scalp
- Hair Count Macrophotography (1cm² Area)
- Instruction and 1st REVIAN/SHAM 10 Minute Treatment
- Adverse Events

A standard macrophotography technique will be provided to all investigational sites. Please refer to the Macrophotography Technique Manual for full instructions on the proper site selection for shaving and tattooing the scalp and macrophotography.

All participating investigators will undergo training on the appropriate use of the REVIAN/SHAM device. Only investigators and co-investigators qualified by training or experience in dermatological conditions of the scalp will be selected for this clinical trial.

All participants will be seen at 8-weeks, 16-, and 26-weeks following enrollment.

3.4.3 Randomization of Treatment Device

All participants will be randomized to one of four study arms. The randomization will be a block design, stratified across the sites and maintained by the local Study Sponsor. Each site will be blinded to the randomization code and will only receive a pre-assigned code to use for each participant at time of enrollment. The code will be pre-assigned to one of the four caps below:

Study Arm 1: Active REVIAN Cap 101Study Arm 2: Active REVIAN Cap 102Study Arm 3: Active REVIAN Cap 103Study Arm 4: Non-Active REVIAN (SHAM) Cap 100

3.4.4 Week 1 Phone Call – (7±3 Days), Visit 3

- Concomitant medication usage
- Adverse Events
- Compliance Follow-up

3.4.5 Week 8 Follow-Up Visit – (56±5 Days), Visit 4

- Subjective Scalp Hair Growth (SSHG) Score
- Physician's Global Assessment (PGA) Score
- Hair Specific Skindex-29 Quality of Life Questionnaire
- Global Photography Image of Two Views (superior and vertex scalp)
- Shave and Tattoo Scalp
- Hair Count Macrophotography (1cm² Area)
- Concomitant medication usage
- Adverse Events
- Compliance Follow-up

3.4.6 Week 16 Follow-Up Visit – (112±10 Days), Visit 5

- Subjective Scalp Hair Growth (SSHG) Score
- Physician's Global Assessment (PGA) Score
- Hair Specific Skindex-29 Quality of Life Score Questionnaire
- Global Photography Image of Two Views (superior and vertex scalp)
- Shave and Tattoo Scalp
- Hair Count Macrophotography (1cm² Area)
- Concomitant medication usage
- Adverse Events
- Compliance Follow up

3.4.7 Week 26 Follow-Up Visit – (182±10 Days), Visit 6

- Physical Exam (including vital signs)
- Subjective Scalp Hair Growth (SSHG) Score:
- Physician's Global Assessment (PGA) Score:
- Hair Specific Skindex-29 Quality of Life Score Questionnaire
- Global Photography Image of Two Views (superior and vertex scalp)
- Shave and Tattoo Scalp
- Hair Count Macrophotography (1cm² Area)
- Concomitant medication usage
- Adverse Events
- Compliance Follow up
- Exit/Termination Form

3.4.8 Unscheduled Visit: Visit within 26-weeks Follow-Up

If the participant returns for a study-related unscheduled visit within the 26-weeks follow-up the following evaluations will be performed:

- Medical treatment
- Adverse event
- Concomitant medication

The following Study Assessment Table provides an overview of activities to be performed at each study visit.

	Visit 1	Visit 2	Visit 3	Visit 4	Visit 5	Visit 6
PROCEDURES	Screening (Day -7)	Baseline (Day 0)	Phone Call (7 ±3 Days)	Week 8 ^{1,2} (56 ±5 Days)	Week 16 ^{1,2} (112 ±10 Days)	Week 26 ^{1,2} (182 ±10 Days)
Informed Consent	X	X				
Demographics	Х	Х				
Medical History	Х	Х				
Medication History	Х	Х				
Inclusion/Exclusion Criteria	Х	Х				
Pregnancy Test (As required)	Х	Х				
Physical Examination		Х				Х
Instruction on Device and 1st Application		Х				
Shave and Tattoo Scalp		Х		X ³	X ³	X ³
Hair Count - Macrophotography (1cm ² Area)		Х		X	Х	Х
Global Assessment Photography (superior and vertex scalp)		Х		X	Х	Х
Growth Assessment and Questionnaires:				-		
(1) Subjective Scalp Hair Growth (SSHG) score ⁴				X	Х	Х
(2) Physician's Global Assessment (sPGA) score ⁴				X	Х	Х
(3) Hair Specific Skindex-29 QoL Questionnaire		Х		X	Х	Х
Blinded Review of Global Photographs (iPGA) ⁴				Х	Х	Х
Follow-up on Compliance and Use of REVIAN/SHAM		Х	X	X	Х	Х
Concomitant Medications		Х	Х	X	Х	Х
Adverse Events		Х	Х	X	Х	Х
End of Study / Termination / Return Device						Х

¹All visit dates are in reference to Baseline, i.e., Visit 4 occurs approximately eight weeks (56 days) after the Baseline Visit.

² Participants will continue treatments throughout the 26-weeks with a daily 10-minute treatment for a total of 56 treatments over 8 weeks, 112 treatments over 16-weeks, and 182 treatments over 26-weeks.

³ Participants may have tattoo ink reapplied to original site of ink dot application at these time periods. ⁴ SSHG, *sPGA* and *iPGA* are not taken at baseline. These assessments are conducted at the follow-up visits only.

3.5 Termination of Participants

Participants may voluntarily withdraw from the study at any time for any reason. The Investigator(s) may elect at any time to withdraw a participant from the study for any reason unrelated to the study treatment if such a decision is in the participant's best medical interest. If a participant discontinues the study, or is withdrawn by the Investigator(s), as much follow-up data as possible will be obtained. The primary reason for termination or discontinuation will be documented on the End of Study case report form. Participants who are withdrawn from the study after treatment for any reason will not be replaced.

Anticipated reasons for not evaluating a participant through the primary endpoint include:

Participant Lost to Follow-Up: Unable to locate participant despite documented attempts to notify the participant via telephone and by certified mail. A participant will not be considered lost to follow-up until the last scheduled follow-up visit (26-week secondary study time point).

Participant Request to Terminate: The participant requests to terminate his/her involvement in the study, therefore withdrawing his/her consent to participate in the study (the investigator must thoroughly document the reasons for termination). Attempts will be made to retrieve any follow-up data, prior to the time point at which voluntary consent was withdrawn, when available, regarding possible AEs at the time of study discontinuation

Participant Death: If possible, an autopsy and/or death certificate should be obtained to document the cause of death.

4.0 SAFETY REPORTING

All adverse events (AEs), whether device- related or not will be recorded and reported. Pain and function symptoms are categorized as complications when a participant's complaint for any of these symptoms results in an unscheduled visit or when a participant presents with new or worsening symptoms as compared to the previous visit.

4.1 Adverse Events

An AE is any undesired clinical response or complication experienced by a participant. All AEs, whether device-related or not, will be recorded on the AE case report forms. Data to be collected will include the description of the AE, onset and resolution dates (or whether the AE is ongoing), severity, management/treatment, outcome, and determination of the relationship to the device and/or procedure. In general, AEs should be reported and classified by the Investigator using a diagnosis. The diagnosis should be confirmed through specific signs, symptoms, and (if necessary) laboratory tests. The Investigator will determine the relationship of the AE to the device or the study procedure.

The Investigator, based on his or her clinical judgment using the following categories (detailed definitions provided in Appendix A), will determine the relationship and severity of the AE to the device and/or treatment procedure:

- *1.* Unrelated: The adverse event is clearly not related
- 2. Possibly related: The adverse event may be related
- 3. Probably related: The adverse event is likely related
- *4. Definite: The adverse event is clearly related*

An AE or an adverse device effect may be mild, moderate or severe.

The term "severe" is used to describe intensity (severity) of a specific event; the mild, moderate and severe definitions are listed below. An event itself, may be of relatively minor medical significance (such as a severe headache). This is not the same as "serious", which is based on participant/event outcomes or action criteria usually associated with events that pose a threat to the participant's life or functioning.

Severity will be determined by the Investigator and coded as to the degree of severity as follows:

- *1. Mild:* Awareness of the event but easily tolerated.
- 2. *Moderate*: Discomfort enough to cause interference withusual activity.
- 3. *Severe*: Inability to carry out usual activity (not necessarily the same as a Serious Adverse Event)

For the purposes of safety reporting in this study, the following definitions will be applied:

- An **adverse event** (AE) is any untoward medical occurrence in a participant whether it is considered device related or not. Diseases, signs, symptoms, or laboratory abnormalities already existing at enrollment are not considered AE's unless they worsen (i.e., increase in intensity or frequency). Surgical procedures themselves are not adverse events; they are therapeutic measures for conditions that require surgery. The condition for which the surgery is required may be an adverse event. Surgical procedures planned prior to enrollment and the conditions leading to these measures are not adverse events.
- An adverse device effect (ADE) is any untoward and unintended response to a medical device, including events arising from insufficient or inadequate instructions for the employment of the device or its use.
- A Serious Adverse Event (SAE) is any AE that 1) results in death, 2) is lifethreatening, 3) results in or prolong hospitalization, 4) results in permanent impairment of a body function or permanent damage to a body structure, 5) necessitates medical or surgical intervention to preclude permanent impairment of a body function or permanent damage to a body structure.

Note: a device malfunction may or may not result in an AE. If a device malfunctions in a manner that causes an AE or a SAE as defined above, then the consequence of the malfunction will be reported as an AE or SAE, as appropriate. However, all device malfunctions will also be tabulated separately, regardless of whether or not an adverse event results from the malfunction.

Any SAE must be reported to the sponsor or designee by the Investigator within 24 hours of first learning about the event. A written report must be sent to the sponsor within ten working days of knowledge of the event to the fax number listed on the Serious Adverse Event Report Form.

The investigator is required to notify the IRB or EC in accordance with local reporting requirements.

4.2 Anticipated Adverse Events

The following AEs may be associated with the REVIAN device:

- Mechanical or electrical failure of the device or components
- Materials of Cap that may cause irritation or tissue reaction
- Allergies to Materials of Cap
- Failure to improve symptoms and/or function
- Hyperpigmentation of the treatment area

4.3 Unanticipated Adverse Device Effects

ISO 14155:2011 (Clinical Investigation of Medical Devices – Good Clinical Practice) defines an unanticipated adverse device effect (UADE) as any *serious* adverse effect on health or safety, any life-threatening problem or death caused by, or associated with a device, if that effect, problem, or death was not previously identified in nature, severity, or degree of incidence in the clinical investigational plan or risk analysis; or any other unanticipated serious problem associated with a device that relates to the rights, safety, or welfare of subjects" (21 CFR 812.3(s)). UADEs must be reported by the clinical investigator to the sponsor and the reviewing IRB/EC, as described below:

- Investigators are required to submit a report of a UADE to the sponsor and the reviewing IRB/HREC as soon as possible, but in no event later than 10 working days after the investigator first learns of the event (§ 812.150(a)(1)).
- PhotonMD will immediately conduct an evaluation of an UADE and report the results of the evaluation to the appropriate regulatory agency, all reviewing IRB/HRECs and participating investigators within 10 working days after first notice of the effect (§§ 812.46(b), 812.150(b)(1)).

All serious reported events will be followed until resolution, stabilization or 30 days after the last participant enrolled has completed the trial, whichever occurs first.

ALL UNANTICIPATED ADVERSE DEVICE EFFECTS AND SERIOUS ADVERSE EVENTS OCCURRING THROUGHOUT THE STUDY PERIOD MUST BE RECORDED ON THE ADVERSE EVENT CRF AND FAXED TO THE STUDY SPONSOR AS SOON AS POSSIBLE (WITHIN 24 HOURS).

4.4 Medical Monitor

To promote early detection of any safety issues routine medical monitoring may be conducted on an ongoing basis. A medical monitor would provide evaluation of safety events at routine intervals. Process flow, supporting documents, and software programming will allow for 21 CFR Part 11 compliant electronic database access, to the medical monitor for real time case review and event adjudication.

The medical monitor may be un-blinded due to the fact the dataset will contain obvious AEs/SAEs specific to the active treatment compared to non-active treatment that will, simply by their presence, un-blind the individual reviewing the data. This process requires the dynamic collection of unmonitored data as soon as an event is reported. The medical monitor will be responsible to review and adjudicate the safety outcome measures and relevant adverse events reported by study investigators. Relevant information and source documents will be provided to assist with their

review and adjudication of events. During regularly scheduled monitoring visits, the clinical research monitors will support the dynamic reporting process through their review of source document information.

The medical monitor would review accumulating safety data to monitor the incidence of Adverse Events and other trends that would warrant modification or termination of the trial. The medical monitor would review the safety outcomes in both arms to ensure that the risks do not exceed the benefits. All reviews conducted by the medical monitor would be reported to the sponsor.

5.0 STATISTICAL ANALYSIS PLAN

5.1 Study Objective/Purpose

The purpose of the study is to collect data on the safety and effectiveness of REVIAN in participants with AGA. In general, for continuous variables, the sample size, mean, standard deviation, and range will be presented. For categorical variables, the number and percentage in each category will be presented.

Primary Efficacy Endpoint: The primary efficacy endpoint of this study is the mean change in hair count from baseline to 16 weeks following the initial application.

Primary Safety Endpoint: The primary safety outcome will be determined by evaluating by the type, frequency, severity, and relatedness of adverse events through the 16 week period for all participants.

Secondary Efficacy Endpoints: The secondary efficacy endpoints include the following:

(1) *Change from Baseline Hair Count*: Like the primary endpoint, change from baseline hair count, will also be assessed at 8 and 26 weeks.

(2) *Rate of Change in Hair Growth*: The rate of change in hair growth at 8, 16 and 26 weeks will be calculated as ratio of change from baseline to baseline.

(3) *Independent Physician's Global Assessment (iPGA)*: An independent reviewer will assess over hair growth from photographs, using PGA scores at weeks 8, 16 and 26. The PGA score hair growth as: -3=greatly decreased, -2=moderately decreased, -1=slightly decreased, 0=no change, 1=slightly increased, 2=moderately increased and 3=greatly increased.

(4) Site Physician's Global Assessment (sPGA): The site investigator will assess over hair growth using the PGA scores at weeks 8, 16 and 26. In addition, the percentage of participants who achieve success as defined by a PGA \geq 2.0 will be summarized by treatment and by weeks.

(5) *Subjective Scalp Hair Growth Score (SSHG)*: Beginning at Week 8, participants will complete a subjective hair growth questionnaire. The participants choose the answer that best fits the following statements:

- 1) Since the start of the study, I can see my bald spot getting smaller. (1="strongly agree" to 5= "strongly disagree")
- 2) Because of the treatment, I have received since the starts if the study, the appearance of my hair is: (1="a lot better" to 5="a lot worse")
- Ever since the start of the study, how would you describe the growth of your hair? (1="greatly increased" to 7="Greatly decreased")
- 4) Ever since the start of the study, how effective do you think the treatment has been in slowing down your hair loss? (1="Very effective" to 4="Not effective at all")
- 5) Compared to the beginning of the study, which statement best describes your

satisfaction with your appearance of:

- a. The hairline in front of your head? (1="very satisfied" to 5="very dissatisfied")
- b. The hair on top of your head? (1="very satisfied" to 5="very dissatisfied")
- c. Your hair overall? (1="very satisfied" to 5="very dissatisfied")

SSHG will be administered at 8 weeks, 16 weeks and 26 weeks

(6) *Hair Specific Skindex-29 Quality of Life Questionnaire (HSSQOL)*: The hair specific Skindex-29 QOL questionnaire is a 29-item questionnaire with 3 domains: 7 questions for symptoms domain, 10 questions emotion domain and 12 questions for function domain. Participants score each question on a scale from 1 (never) to 5 (all the time). Scores are then summed within each domain and overall. HSSQOL will be administered at baseline, 8, 16 and 26 weeks.

(7) Overall Treatment Success (OTS): Overall treatment success will be defined as the number of participants who achieve \geq 50% reduction in overall QOL scores, plus reported SSHG \geq 2 on every question.

Secondary Safety Endpoint: The primary safety outcome will be determined by evaluating by the type, frequency, severity, and relatedness of adverse events through the 26-week period for all participants.

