2.4 Study Endpoints

2.4.1 Primary Efficacy Endpoint:

The primary efficacy endpoint of this study is mean change in hair count from baseline to 16 weeks following the initial application at baseline.

2.4.2 Secondary Efficacy Endpoints:

Secondary efficacy endpoints will be determined using the following outcome measurement tools to evaluate changes at each follow up visit compared to baseline:

- 1. *Change from Baseline Hair Count*: Like the primary endpoint, change from baseline hair count, will also be assessed at 8 and 26 weeks.
- 2. Rate of Change in Hair Growth: The rate of change in hair growth at 8, 16, and 26 weeks will be calculated as a ratio of change from baseline to baseline.
- 3. Independent Physician's Global Assessment (iPGA): An independent reviewer will assess over hair growth over baseline from photographs, using PGA scores at weeks 8, 16 and 26. The PGA score hair growth as: -3=greatly decreased, -2=moderately decreased, -1=slightly decreased, 0=no change, 1=slightly increased, 2=moderately increased and 3=greatly increased
- 4. *Site Physician's Global Assessment (sPGA)*: The site investigator will assess over hair growth using the PGA scores at weeks 8, 16, and 26.

In addition, the percentage of participants who achieve success as defined by a PGA ≥ 2 will be summarized by treatment and by weeks.

- 5. *Subjective Scalp Hair Growth Score (SSHG): SSHG* will be administered beginning at 8 weeks and then at 16 and 26 weeks.
- 6. *Hair Specific Skindex-29 Quality of Life Score Questionnaire (HSSQOL)*: The hair specific Skindex-29 QOL questionnaire will be administered at baseline, 8, 16, and 26 weeks.
- 7. Overall Treatment Success (OTS): Overall treatment success will be defined as the number of participants who achieve ≥50% reduction in overall QOL scores, plus reported SSHG ≥2 on every question.

2.4.3 Primary Safety Endpoint(s):

At each follow-up visit, participants will be interviewed to determine if any adverse events (AEs) were experienced since the previous follow-up visit. If deemed necessary, a physical assessment may be performed for any participant experiencing a serious adverse event or as required by the Principal Investigator. The primary safety outcomes will be determined by evaluating by the type, frequency, severity, and relatedness of adverse events through the 26-week period for all participants.

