2.6 Participant Eligibility Criteria

Inclusion Criteria:

Candidates for this study must meet ALL of the following criteria:

- 1. Male and Female participants between 18 and 65 years of age
- 2. Must be able to read and speak English.
- 3. Participants who are able to give voluntary, written informed consent to participate in this clinical investigation and from whom consent has been obtained.
- 4. Participants, who, in the opinion of the Clinical Investigator, are able to understand this clinical investigation, cooperate with the investigational procedures and are willing to return for all the required follow-up visits.
- 5. Participant must be able to visit clinic site at 8-, 16- and 26-weeks study visits and be available by phone at 4 weeks.
- 6. Participant must have the ability to communicate effectively with study personnel in person or over the phone.
- 7. Participant must have diagnosis of Androgenic Alopecia (pattern hair loss).
- 8. Participant must have active hair loss consistent with Grades IIa to V, based on Norwood-Hamilton Scale or Ludwig-Savin Scale I-1 to I-4, II -1, II-2 or frontal and Grades I - IV using Fitzpatrick Skin Type Scale.
- 9. Participant's hair must be at least 1 inch in length. The hair style and length shall be the same for each follow-up visit. Participants will be instructed to not have their hair cut/styled within 5 days prior to a follow-up visit.
- 10. Participant is willing to have a dot tattoo placed on or around the target area of the scalp.
- 11. Participant is willing to undergo all study procedures including consent for global photographs of hair loss/growth and a 1 mm tattoo to mark the macrophotography site along the indicated transition area of the scalp between the hairline and the balding/thinning vertex area.
- 12. Participant is willing to avoid the use of wigs, hairpieces, and/or hair extensions during the study period.
- 13. Hair Specific Skindex-29 Quality of Life total overall score of \geq 45.
- 14. Participant is willing to maintain their natural hair colour or including the use of coloring throughout the study period.
- 15. Participant agrees to refrain from using all other hair growth products or treatments (oral or topical medication including over the counter herbal medications, or Dutasteride) during the study period.
- 16. Participant has the ability to utilize a Bluetooth device and application on a smart device connected to Wi-Fi.

Exclusion Criteria:

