APPENDIX B: HAIR SPECIFIC SKINDEX-29 QUALITY OF LIFE QUESTIONNAIRE

Scoring:

Sx: Symptom (7-35), Em: Emotion (10-50), Fx: Function (12-60) Total Scoring = (29-145)

APPENDIX C: Physician's Global Assessment (PGA) Scoring and Subjective Scalp Hair Growth (SSHG) Evaluations

A Canfield stereotactic positioning device will be used for obtaining global photographs where the participant's chin and forehead are fixed, and on which a given camera and flash device are mounted to standardize the view, magnification and lighting at consecutive study visits. Participants will be asked to keep the same hair style and colour and the coordinators attempt to duplicate baseline hair parting and combing in subsequent follow-up visits. Two standard views (superior and vertex) will be taken at baseline, 8-, 16, and 26-weeks (Figure 5). The digital images will be graded. Paired baseline and post-treatment photographs will be evaluated by each site study doctor (at the Week 8, 16 & 26 follow up visits) in order to provide a physician global assessment (*sPGA*) score.

In addition, the photographs will then be independently reviewed by two blinded evaluators, to evaluate the independent physician's global assessment (iPGA)

The PGA score used is the standardized 7-point rating scale (-3 = greatly decreased, -2 = moderately decreased, -1 = slightly decreased, 0 = no change, +1 = slightly increased, +2 = moderately increased, +3 = greatly increased increased).

Figure 5. Global Photography, demonstrating fixation of the participant on a brow and chin rest with the camera mounted on a rotating arm.

Participants will be asked to assess subjective scalp hair growth (SSHG). They will be provided with the following questionnaire at each follow up visit (8, 16 and 26 weeks after baseline).

Subjective Scalp Hair Growth (SSHG)

1. Since the start of the study, I can see my bald spot getting smaller

Strongly Agree	Agree	No opinion either way	Disagree	Strongly Disagree
1	2	3	4	5

2. Because of the treatment I have received since the start of the study, the appearance of my hair is:

A lot better	Somewhat better	A little better	Same	A little worse	Somewhat worse	A lot worse
1	2	3	4	5	6	7

3. Ever since the start of the study, how would you describe the growth of your hair?

Greatly increased	Moderately increased	Slightly increased	No change	Slightly decreased	Moderately decreased	Greatly decreased
1	2	3	4	5	6	7

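### On the summed Skindex score (range 29-145), the 50% reduction required for Overall Treatment Success cannot be reached from entry scores of 45-57, and for everyone else it means removing 62.5-100% of the impairment above the floor

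*Combined protocol and SAP*

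**What the plan says.** OTS is a secondary efficacy endpoint in the protocol synopsis, 2.4.2(7) and 5.1(7). Section 2.4.2(7) introduces it as a count: "Overall treatment success will be defined as the number of participants who achieve" two conditions together. The quality-of-life condition is at least a "50% reduction in overall QOL scores, plus reported SSHG" at a stated level on every question.

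The score is defined immediately before this, in 5.1(6). The instrument is a "29-item questionnaire with 3 domains: 7 questions for symptoms domain, 10 questions emotion domain and 12 questions for function domain". Of the coding it says: "Participants score each question on a scale from 1 (never) to 5 (all the time"). Of the total: "Scores are then summed within each domain and overall". Section 3.4.2 gives the ranges, ending "symptom (7-35) categories with total scoring ranging from 29-145", and Appendix B agrees: "Total Scoring = (29-145"). The SAP also sums the items (section 8 endpoint list, and 10.2), derives no variables (8.7) and plans no transformations (8.8).

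Inclusion criterion 13 in 2.6 requires a "Hair Specific Skindex-29 Quality of Life total overall score of" at least 45. Section 3.4.2 repeats this.

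Section 3.4.2 also says that responses are converted to a 100-point scale, and quotes severity cut-offs that include 52 for symptoms and 44 overall. The two scorings are not reconciled anywhere.

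**The concern.** A percentage reduction has a plain meaning only when the scale starts at zero. This sum starts at 29, because the best answer to each item scores 1. Halving the sum is therefore a much larger demand than halving the impairment, and near the entry limit it cannot be done at all. A participant who enters at 45 and later answers never to all 29 items would be recorded as not successful.

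If OTS is calculated this way, its rate depends on where participants start on the scale as well as on how much they benefit. Anyone barred by the baseline score is a non-responder in every arm. If a fraction x of participants is barred, no arm's OTS rate can exceed 1 − x. The documents do not give x. Taking 10%, 30% or 50% purely as assumptions, the ceiling would be 90%, 70% or 50%.

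The SSHG half of OTS is a separate matter, and nothing here depends on it.

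**Working it through.** **Inputs.** 29 items (7 symptom, 10 emotion, 12 function), coded 1-5 (5.1(6)). Overall score = sum (5.1(6), Appendix B, SAP 8 and 10.2). Entry score ≥ 45 (2.6, 3.4.2). Success requires a fall of ≥ 50% (2.4.2(7), 5.1(7)).

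**Plan's own figure.** Lowest and highest sums: symptoms 7×1 to 7×5 = 7-35; emotion 10-50; function 12-60; total 29-145. This matches 3.4.2 and Appendix B.

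**Feasibility.** With baseline sum B, success needs a follow-up sum ≤ B/2. No follow-up sum can be below 29, so B/2 ≥ 29, that is B ≥ 58. All 13 whole-number entry scores from 45 to 57 fail this.

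**Size of the demand.** The largest possible fall is (B − 29)/B. The share of above-floor impairment that must be removed is (B/2)/(B − 29).

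| Baseline sum B | Follow-up must be ≤ B/2 | Largest possible fall | Share of above-floor impairment required |
|---|---|---|---|
| 45 | 22.5 | 16/45 = 35.6% | not reachable |
| 57 | 28.5 | 28/57 = 49.1% | not reachable |
| 58 | 29 | 29/58 = 50.0% | 29/29 = 100% |
| 82 | 41 | 53/82 = 64.6% | 41/53 = 77.4% |
| 87 | 43.5 | 58/87 = 66.7% | 43.5/58 = 75.0% |
| 100 | 50 | 71/100 = 71.0% | 50/71 = 70.4% |
| 145 | 72.5 | 116/145 = 80.0% | 72.5/116 = 62.5% |

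Since scores are whole numbers, a baseline of 145 actually needs a fall of 73, which is 73/116 = 62.9%. The lowest share with whole-number scores is at 144: 72/115 = 62.6%.

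**Effect of the 100-point text.** Assume the total is rescaled linearly as (sum − 29)/116 × 100.

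- *Entry and OTS both on the sum:* entry scores 45-57 are barred, and the rest of the table applies as shown.
- *Entry on 100 points, OTS on the sum:* 45 points corresponds to 29 + 0.45×116 = 81.2, so the raw entry sum is 82 or more. Nobody is barred, but 50% means 77.4% (at 82) down to 62.5% (at 145) of above-floor impairment.
- *OTS on 100 points:* the floor is 0, every entrant can halve the score, and the defect vanishes.

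**The case against.** The strongest objection is that the scoring is unresolved. Section 3.4.2 describes the 100-point scale and then says that the overall score will be used to show improvement during the trial, which is what OTS measures. The entry value of 45 also sits next to a quoted overall cut-off of 44. The list containing that cut-off must be on the 100-point scale, because its symptom value of 52 exceeds the symptom-sum maximum of 35. On that reading the group entering at raw sums of 45-57 may not exist. This stands as a limit on the point: the barred group is a consequence of the sum scoring, not an established fact about the trial. It does not remove the point, because the definition next to OTS, Appendix B and the SAP all use the sum.

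A reader might also infer that the rule will hide a real difference between an active cap and sham. The documents do not support that. OTS is missing from the SAP's endpoint list, its section 10 analyses and its list of tables, so no OTS comparison is specified. No baseline Skindex distribution is given, so the number affected could be negligible or large. From 58 upward, success still depends on improvement, against a stricter threshold. The overall Skindex score is analysed separately in SAP 10.2 whatever happens to OTS.

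It could also be said that a stricter threshold is a legitimate choice. That is fair for the upper part of the scale, but the documents do not present it as one, and it cannot justify a threshold beyond the end of the scale.

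**Conclusion.** The point holds, conditionally on the sum scoring that 5.1(6), Appendix B and the SAP state. On that scoring the OTS quality-of-life condition is impossible for entry sums of 45-57, and its nominal 50% means 62.5-100% of above-floor impairment for everyone else. If only the entry value is on the 100-point scale, nobody is barred and the range is about 62.5-77%. If OTS itself is on that scale, there is no defect.

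The arithmetic is certain. Which scoring is intended, and how many participants would be affected, cannot be determined from the documents. The consequence is limited to one secondary responder endpoint that the protocol lists and the SAP does not carry forward. The primary hair-count analysis is untouched. It is worth correcting because anyone who calculates OTS from the protocol as written would meet the problem.

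**What to change.** 1. In the synopsis, 2.4.2(7) and 5.1(7), define the quality-of-life part of OTS as (baseline sum − follow-up sum)/(baseline sum − 29) ≥ 50%. This is the same as a 50% reduction in the total rescaled as (sum − 29)/116 × 100. Write the formula out: 3.4.2 does not say how its 100-point overall score is formed, and an average of three rescaled domain scores (7, 10 and 12 items) would generally differ from the rescaled total.
2. Reconcile 2.6 with 3.4.2 by stating which scale the entry value of 45 is on.
3. If OTS is to be reported, add it to the SAP's endpoints, analyses and tables, and align SAP 8.7 and 8.8, which currently exclude derived variables and transformations.

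No new data are needed, but the edits touch several sections of both documents. The target sum becomes 29 + (B − 29)/2, so a baseline of 45 needs 37, 57 needs 43 and 145 needs 87. The cost is that OTS becomes easier to reach in all arms. If entry is on the raw sum, a participant starting at 45 would meet this part with a fall of 8 points, which is 8/116 = 6.9% of the scale range. The sponsor should accept that knowingly.
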